**Table 2: Analysis Windows**

Analysis Visit	Range	Target Day
Baseline	Day $\leq$ 1	Day 1
Day 28 (Week 4)	Day 2 to Day 42	Day 28
Day 56 (Week 8)	Day 43 to Day 70	Day 56
Day 84 (Week 12)	Day 71 to min (Day 91, TRTEDT+7)	Day 84
Day 112 (Follow-Up)	> min (Day 91, TRTEDT+7)	Day 112

+TRTEDT – date of last study medication

The Follow-Up assessment will be the last assessment available that is at least seven days after the end of treatment. Should no post treatment assessments be available the subject will not have a follow-up assessment. Any assessments reported after the date of last study medication will be considered as a follow-up assessment.

For other efficacy and safety endpoints, the study visits as specified in the protocol will be utilized as analysis visits.

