6.5.8 Day 84 Visit

The following procedures and evaluations may be performed at the clinic or at the subject's home by the mobile research nurse on Day 84 (\pm 3 days):

- Cough severity VAS
- Vital signs
- Study drug dosing
 - Observe AM dose (before 10 am)
- Attach and activate Day 84 cough monitor (**AFTER DOSING**)

- Study Drug - collect/perform accountability for Days 57–84 bottles
- Review IVRS/IWRS Days 57–84 dosing diary entries
- Record all AEs
- Record all concomitant medication use
- Remind subject about Day 85 Visit at clinic

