## 8.4 Data Handling Rules for Cough Analysis

The 24-hour cough frequency (coughs per hour) for a specified visit is calculated as:

$$\text{24-hour cough frequency} = \frac{\text{total number of cough events over 24-hour monitoring period}}{\text{Total duration (in hours) over 24-hour monitoring period}}$$

The awake cough frequency (coughs per hour) is defined as below:

$$\text{Awake cough frequency} = \frac{\text{total number of cough events during the monitoring period the subjects is awake}}{\text{Total duration (in hours) for the monitoring period the subject is awake}}$$

Awake duration (hours) is time between waking up and sleep during the 24-hour monitoring period.

The cough data will contain all cough events occurring during that 24-hour monitoring period as well as the information about “sleep time” and “awake time”. Any session with duration of

recording < 4 hours will be considered as missing. Repeated monitoring may be conducted when there is an equipment failure or an unacceptable evaluation from the initial monitoring.

In general, each 24-hour session is composed by an awake monitoring period and a sleep monitoring period. If a subject did not wake up before the end of the recording session, it will be assumed that the subject slept for the rest of the session. The session will have missing awake time, and the rest of session will be considered under the sleep monitoring period. For any session with both sleep time and awake time missing, the entire 24-hour session will be considered under the awake monitoring period, unless the session has early termination of recording.

On each collection day, the cough count, the actual cough monitoring duration (in hours), and the coughs per hour will be derived for the total 24-hour period, the awake period, and the sleep period, respectively.

The percent change in 24-hour coughs per hour at each specific visit is defined as below:

percent change in 24-hour cough frequency =

$$[(\text{change from baseline in 24-hour cough frequency} \times 100) / (\text{baseline 24-hour cough frequency})]$$

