### 9.6.2.1 Analyses of Primary Endpoint

#### A. Primary Analysis - Mixed Model Repeated Measures Analysis of Log Transformed 24-hour Cough Frequency:

As the change in 24-hour cough frequency may have a skewed and wide distribution, the primary analysis for the primary endpoint will be on the natural log scale of the cough frequency data. The difference between serlopitant 5 mg and placebo will be estimated using a mixed effect repeated measures (MMRM) model. The model will include fixed effects for treatment group, visit, country, sex, the treatment-by-visit interaction, and the log-transformed baseline value as a covariate. The MMRM model will use all available 24-hour cough frequency data on Day 28, 56, and 84. An unstructured covariance structure will be applied for MMRM. In case the model will not converge with the unstructured covariance structure, the heterogeneous compound symmetry (CSH) will be used instead. Furthermore, if the model fails to converge with CSH, the heterogeneous Toeplitz structure (TOEPH) will be used. If the unstructured covariance structure will be used, the denominator degrees of freedom will be computed using the Kenward-Roger method. In case of other covariance structures, the BETWITHIN (SAS®) option will be used for the denominator degrees of freedom. Contrasts will be constructed to compare each of the three serlopitant treatment groups to the placebo group at each visit. The least-squares (LS) mean change from baseline (on the log scale) with the associated standard errors will be displayed for each treatment group. Estimated treatment differences (serlopitant vs. placebo) along with corresponding one-sided 95% CIs and p-values will also be presented at each post-baseline timepoint.

In addition, the geometric mean of 24-hour cough frequency will be presented by treatment and by visit. The percent difference change between serlopitant and placebo will be estimated by  $100(e^{\text{diff}} - 1)$ , where diff is the difference provided by the analysis of the log-transformed variable. A sample of SAS code for MMRM analysis is provided in Appendix A.

An observation of zero coughs per hour will be replaced by a cough rate of 0.1 for the calculation of geometric means.

Missing data, in the assessment of the primary hypothesis, is assumed as missing at random (MAR). This assumption will be assessed with a missing data sensitivity analysis (see Section 9.6.5 Sensitivity analysis of the primary endpoint).

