## APPENDIX C: STUDY VISIT MAP WITH MATCHED INTERVAL ID

## Study Visits and Matched Interval IDs in Datasets

Study Procedures	Screening	Baseline	Treatment Period						Follow-up	
	Screening	Day 0 Study Day -1	Day 1	Day 14	Day 28	Day 56	Day 84	Day 85 /ETD	Day 112	Day 113
VISITNUM	1	2	3	4	5	6	7	8	9	10
Interval ID	148	149	150	151	155	156	157	158	159	160
Study Visit Window			1 ST DAY DOSING	± 3	± 3	± 3	± 3	± 3	± 3	± 3
Vital Sign Data a	X	X	X		X	X	X	X		X
Cough Severity VAS Monitoring Data a	X	X			X	X	X	X	X	X
Telephone Contact Data a				X						
Cough Monitoring Data b		X			X	X	X		X	

a Data collected at visits marked as X. Visit dates will be derived based on the following three datasets: vital sign, cough severity VAS monitoring, and telephone contact. If there is any discrepancy in a visit date, the date recorded in vital sign dataset will be considered as the primary date.

b The cough monitoring data has regular visits labeled as Baseline, Day28, Day56, Day84, and Day112, and the repeated visits labeled as Baseline-R, Day28-R, Day56-R, Day84-R and Day112-R. Both regular and repeated records at the specific visit will be included in analysis data. Repeated evaluations are usually due to equipment failures or unacceptable initial evaluations.

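### SAP 7.3 assigns a cough recording made 1 to 7 days after last dose both to the Day 84 window (Table 2) and to follow-up (closing sentence), so the status of a repeat Day 84 recording is undefined

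*SAP*

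**What the plan says.** SAP 7.3 assigns cough recordings to analysis visits by study day. In Table 2 the Day 84 range is "Day 71 to min (Day 91, TRTEDT+7"), where TRTEDT is the date of last study medication, and Follow-Up is anything later than that same limit. The Day 28 range (Days 2 to 42) and the Day 56 range ("Day 43 to Day 70") have no limit tied to last dose.

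Two sentences below the table also define follow-up:

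- "The Follow-Up assessment will be the last assessment available that is at least seven days after the end of treatment".
- "Any assessments reported after the date of last study medication will be considered as a follow-up assessment".

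No order of precedence is given. The general rule above the table takes the recording closest to the target day, and the first one if two are equally close.

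Repeat recordings are planned. SAP 8.4 states: "Repeated monitoring may be conducted when there is an equipment failure or an unacceptable evaluation from the initial monitoring". SAP Appendix C, footnote b, labels the repeats "Baseline-R, Day28-R, Day56-R, Day84-R and Day112-R" and adds that regular and repeated records at a visit both enter the analysis data. Protocol 6.5.8 lists, at the Day 84 visit, "Study Drug - collect/perform accountability for Days" 57–84 bottles. For the primary analysis, SAP 9.6.2.1 says "The MMRM model will use all available 24-hour cough frequency data on Day 28, 56, and 84".

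**The concern.** For a recording dated after last dose but within the Table 2 limit, the table and the closing sentence give opposite answers. If the closing sentence governs, the seven-day allowance in the Day 84 row can never apply to any recording made after last dose. If the table governs, the closing sentence is wrong.

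The plan foresees recordings of this kind. The bottles are collected at the Day 84 visit, so a Day 84 repeat on a later date falls after last dose. Under Table 2 it can supply the Week 12 value. Under the closing sentence it cannot. If the initial session gave no usable value, the subject then has no Day 84 value for the primary endpoint, for awake cough frequency, or for the two 30% responder endpoints. The VAS endpoint is not affected, because 7.3 uses protocol visits for the other efficacy measures.

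Two programmers could follow 7.3 in good faith and build different primary datasets. If the choice is left open, it may be made after treatment codes are known.

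**Working it through.** **1. Window rules by day.** Let T be the day of last dose, D the recording day, and c = min(91, T+7).

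| Last dose (T) | Table 2: Day 84 through | Closing sentence: follow-up from | Days in conflict |
|---|---|---|---|
| 81 | Day 88 | Day 82 | 82–88 (7 days) |
| 84 | Day 91 | Day 85 | 85–91 (7 days) |
| 87 | Day 91 | Day 88 | 88–91 (4 days) |

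These rows cover the ±3-day visit window. For every T from 1 to 87 and every D from T+1 to T+7 there are 87 × 7 = 609 pairs. Table 2 places 603 of them in a treatment window only; the exceptions are 1 + 2 + 3 = 6 pairs for T = 85, 86 and 87, which lie beyond Day 91. The closing sentence places all 609 in follow-up. This grid tests the logic. It does not forecast how many recordings will occur.

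**2. The sentence on at least seven days.** For T up to 84 it differs from Table 2 only at D = T+7. With T = 84, Day 91 is Day 84 data in the table and follow-up in the sentence.

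**3. Planning figure, reproduced.** Inputs from SAP 8.2: CV 0.64, ratio 0.75, one-sided alpha 0.05, power 90%, dropout 15%.

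- Log SD = sqrt(ln(1 + 0.64²)) = 0.586. Effect = |ln 0.75| = 0.2877.
- The t-test needs 72 per arm, with power 90.1%.
- 72 / 0.85 = 84.7, so 85 per arm and 170 in total, as stated.
- SE = 0.586 × sqrt(2/72) = 0.0977.

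**4. Cost of losing Day 84 values.** The documents give no repeat rate. Assume that a fraction f of completers, 2% to 10%, lose the value. Completers number 170 × 0.85 = 144.5, so this is 2.9 to 14.5 values. The MMRM recovers part of the loss from Days 28 and 56. With equal correlation rho between visits (assumed 0.5 to 0.8):

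- R² = 2rho² / (1 + rho) = 0.333 at rho 0.5 and 0.711 at rho 0.8.
- Variance factor = 1 + [f / (1 − f)] × (1 − R²).
- Example, f = 10% and rho = 0.5: 1 + 0.1111 × 0.667 = 1.074; SE factor = sqrt(1.074) = 1.036.

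| f | SE factor (rho 0.8 to 0.5) | Power (rho 0.8 to 0.5) |
|---|---|---|
| 0 | 1 | 90.1% |
| 2% | 1.003–1.007 | 89.9%–89.8% |
| 5% | 1.008–1.017 | 89.7%–89.2% |
| 10% | 1.016–1.036 | 89.3%–88.2% |

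If nothing were recovered from earlier visits, a 10% loss would leave about 65 per arm and power of 87.3%.

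**5. Overlap of the early windows with Follow-Up.** By the ranges alone, Day 28 overlaps Follow-Up when T is 34 or earlier, and Day 56 does so when T is 62 or earlier. Over T = 1–87 and D = 2–126 (87 × 125 = 10,875 pairs), 1,953 pairs meet two windows. With the Day 28 and Day 56 ranges capped at T+7, no pair meets two windows and none meets zero.

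**The case against.** The best reply is that the intention is clear. Table 2 allows seven days after last dose, and Appendix C puts repeats into the analysis data under their visit label. A programmer would have to set both aside to lose a Day84-R value. That is fair as evidence of intent, but 7.3 assigns cough recordings by day, and nothing says that a label or the table overrides the closing sentence.

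The size is also bounded, and this objection stands. A repeat later than min(Day 91, TRTEDT+7) is follow-up under both rules. Only sessions shorter than 4 hours are set to missing, so an initial session of 4 hours or more can still supply the Day 84 value, and the closest-to-target rule may prefer it. The 2.9 to 14.5 values are therefore an upper bound for the assumed repeat rates.

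A reader might infer three stronger points. The documents do not support them.

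- *Three separate cut-offs in conflict.* The sentence on at least seven days mainly selects which recording supplies the follow-up value, and it departs from Table 2 essentially at exactly seven days. The conflict that matters is between the table and the closing sentence.
- *Off-drug recordings from early stoppers modelled as Week 4 or Week 8 data.* This requires such recordings to exist and the closing sentence to be ignored. No monitor is attached at the early discontinuation visit, and SAP Appendix B, footnote r, waives Day 112 for early stoppers. Protocol 6.5.9 does list scheduling Day 112, but that list is shared with the regular Day 85 visit and includes items that cannot apply to every early stopper.
- *Regular Day 84 recordings at risk.* The monitor is attached after the observed dose at the same visit, so the recording is not dated after last dose.

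**Conclusion.** The contradiction is real and bears on the primary dataset, but it is minor. It concerns recordings from the day after last dose to min(Day 91, TRTEDT+7), in practice mainly Day84-R repeats. Under an assumed 2% to 10% loss of Day 84 values and visit correlations of 0.5 to 0.8, power falls from 90.1% to no lower than 88.2%. Both ranges are assumptions, and the loss is an upper bound for the stated repeat rates. The sample size is unaffected. Following the closing sentence costs a little precision; nothing here points to a false positive. The reason to act is that the rule should be settled before unblinding.

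**What to change.** In SAP 7.3:

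1. Delete the closing sentence on assessments after last study medication and the sentence on at least seven days. Replace them with a statement that Table 2 governs and that any recording later than min(Day 91, TRTEDT+7) is follow-up.
2. As a consistency edit, change Day 28 to Day 2 to min(Day 42, TRTEDT+7) and Day 56 to Day 43 to min(Day 70, TRTEDT+7). No recording then meets two windows. This matters only if early stoppers are recorded off drug, which footnote r makes unlikely.
3. State one selection rule for the Follow-Up row, either the last available recording or the one closest to Day 112, and say that it overrides the general closest-to-target rule if it differs.

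The cost is SAP wording only, with no added visit or recording. One consequence should be accepted openly: a subject with no recording by TRTEDT+7 has no treatment-window value and falls outside the FAS. SAP 6.1 already implies this, since it requires a post-baseline observation within the treatment period.

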6.5.9 Day 85/Early Treatment Discontinuation Visit

The following procedures and evaluations will be performed at the clinic on Day 85 or within 7 days of the last dose of study drug for subjects who discontinue study drug treatment early.

At this visit, the following procedures and assessments are to be performed:

- Cough severity VAS
- PGIC
- LCQ
- Vital signs
- Weight
- Collect Day 84 cough monitor
- Complete physical exam
- ECG (12 lead)
- Laboratory tests
 - Reproductive endocrine labs for females under 55 years of age at time of consent
 - Endocrine
 - Hematology
 - Chemistry
 - Urinalysis
 - Urine pregnancy test for females of childbearing potential
 - Urine drug screen
- Contact IWRS to register Day 85 end of treatment visit
- Review IVRS/IWRS Days 57–84 dosing diary entries
- The following will be completed by the Investigator (MD or DO):

- CGIC
- Study drug - collect/performance accountability for Days 57–84 bottles (**early treatment discontinuation visit only**)
- Record all AEs
- Record all concomitant medication use
- Schedule Day 112 visit at clinic or at subject's home
- Schedule Day 113 visit at clinic

6.5.10 *Day 112 Follow-up Visit*

Subjects will return to the clinic or be visited by a mobile research nurse on Day 112 (± 3 days) for the following procedures and evaluations:

- Cough severity VAS
- Record all AEs
- Record all concomitant medication use
- Attach and activate cough monitor
 - Cough monitor will be collected the following day by a courier service and delivered to the clinic
- Contact IWRS to register the Day 112 Follow-up visit
- Remind subject about Day 113 visit at clinic

6.5.11 *Day 113 Follow-up Visit*

Subjects will return to the clinic on Day 113 for the following procedures and evaluations:

- Vital signs
- Collect Day 112 cough monitor
- Cough severity VAS
- LCQ
- Contact IWRS to register the Day 113 Follow-up visit
- Complete physical exam
- ECG (12-lead)

- Laboratory tests
 - Reproductive endocrine labs for females under 55 years of age at time of consent
 - Endocrine
 - Hematology
 - Chemistry
 - Urinalysis
 - Urine pregnancy test for females of childbearing potential
 - Urine drug screen
- Record all AEs
- Record all concomitant medication use

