### 7.3 Analysis Windows

The analysis windows used to report cough frequency endpoints are outlined in Table . If more than one assessment is available within the range the assessment closest to the target day is reported for the analyses window. If two observations exist with the same distance to the target day, the first observation is used.

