#### **9.6.4.3 Leicester Cough Questionnaire (LCQ)**

The Leicester cough questionnaire (LCQ) instrument will be assessed at Baseline (Study Day0), Day 28, Day 56, 85/Early Termination, and Follow-up (Day 113). There are three domains in the LCQ instrument: Physical (items 1, 2, 3, 9, 10, 11, 14 and 15), Psychological (4, 5, 6, 12, 13, 16, and 17), and Social (7, 8, 18, 19). For each domain, the domain score (range 1-7) is the sum of individual item score within the domain divided by the number of items in the domain; total LCQ score (range 3-21) is the sum of the three domain scores. Baseline LCQ is defined as the LCQ collected at Baseline (Study Day -1).

For each domain (physical, psychological, and social) and total LCQ score, change from baseline will be analyzed in similar manner as indicated for the primary endpoint in Section 9.6.2.1. Line plots of individual subject baseline and post treatment scores will be generated by treatment group and serlopitant for each domain and total LCQ scores.

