#### **9.6.4.4 Patient's Global Impression of Change**

The self-report measure Patient's Global Impression of Change (PGIC) reflects a patient's belief about the efficacy of treatment. PGIC is a 7-point scale depicting a patient's rating of overall improvement. Patients rate their change as "very much improved," "much improved," "minimally improved," "no change," "minimally worse," "much worse," or "very much worse." The counts and proportions of ordered responses to the subject's global perception of change will be computed for each treatment group on Day 28, Day 56, Day 85/ETD. Proportion of subjects with improvements (either "very much improved" or "much improved" on the PGIC scale) will also be presented. The distribution of responses will be compared between each of the serlopitant treatment groups and placebo using the stratified Cochran Mantel Haenszel (CMH) test (stratified by country and sex, unless stated otherwise).

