#### **9.6.4.5 Clinician's Global Impression of Change**

The Clinician's Global Impression of Change (CGIC) reflects a clinician's belief about the efficacy of treatment. CGIC has the same 7-point scale like PGIC.

CGIC will be evaluated at Day 85/ETD. Similar analysis for PGIC will be applied for CGIC.

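### LCQ, PGIC and CGIC from early-discontinuation visits are pooled with true Day 85 values, because the SAP's study-day windows cover cough frequency only

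*SAP*

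**What the plan says.** **Windows.** SAP 7.3 limits its study-day windows to one kind of data: "The analysis windows used to report cough frequency endpoints are outlined in Table" 2. For Week 12 the range runs from Day 71 to the earlier of Day 91 and seven days after the last dose. Below the table the SAP adds: "For other efficacy and safety endpoints, the study visits as specified in the protocol will be utilized as analysis visits".

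**The visit.** Protocol 6.5.9 defines a single visit, held "on Day 85 or within 7 days of the last dose of study drug for subjects who discontinue study drug treatment early". LCQ, PGIC and CGIC are all collected there. SAP Appendix C gives both occasions one code (VISITNUM 8, Interval ID 158). Under SAP 3.0, early stopping can occur at any point in the treatment period.

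**The analyses.**
- LCQ (SAP 9.6.4.3): the post-baseline on-treatment visits are Day 28, Day 56 and the combined Day 85/early-termination visit, and "change from baseline will be analyzed in similar manner as indicated for the primary endpoint in Section 9.6.2.1". That section is the MMRM with three post-baseline visits and a missing-at-random assumption.
- PGIC (SAP 9.6.4.4): counts and proportions "will be computed for each treatment group on Day 28, Day 56, Day 85/ETD", with a stratified CMH comparison.
- CGIC (SAP 9.6.4.5): "CGIC will be evaluated at Day 85/ETD", and at no other visit.

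Nothing in either document reassigns ETD values of these three endpoints by study day, reports them apart or excludes them.

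**The concern.** Take a subject who stops on Day 33 and attends ETD on Day 38. The subject has an LCQ at Day 28, none at Day 56, and one under Day 85/ETD. The model reads that last score, given in the sixth week, as an end-of-treatment outcome. In effect this carries an early observation forward inside a model that is justified by missing at random. The subject's cough frequency is handled differently: no monitor is attached at the ETD visit, so Week 12 is simply missing.

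Three things are at stake:

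- The end-of-treatment LCQ and PGIC results mix treatment durations, so they do not describe the same time point as the primary endpoint that they support. Improving cough-specific quality of life is a stated secondary objective.
- Stopping may differ by arm. Protocol 5.6 lists likely related Grade 2 or higher events among the reasons for discontinuation. The mixing can then differ by arm too and shift the comparison.
- CGIC has no other time point, so the plan yields no CGIC result for Day 85 alone.

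**Working it through.** **1. The plan's own figure.** Inputs from SAP 8.2: ratio 0.75, CV 0.64, one-sided 0.05, 90% power, 15% dropout.
- Log-scale SD = √ln(1 + 0.64²) = 0.5859. Log difference = |ln 0.75| = 0.2877.
- n per arm = 2 × (1.645 + 1.282)² × 0.5859² / 0.2877² ≈ 71.1, so 72. A noncentral-t check at 72 gives 90.1% power.
- 72 / 0.85 = 84.7, so 85 per arm and 170 in total. This reproduces the plan, so 15% of 85 is the right base for what follows.

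**2. Who can contribute a mistimed value.** Efficacy uses the FAS (SAP 8.1), which requires an on-treatment cough recording (SAP 6.1). The first is scheduled at Day 28 ± 3. Subjects who stop before it normally leave the FAS.

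**3. How many.** Assumptions: stop days uniform over Days 1 to 84, every stopper attends ETD, and all other subjects are in the FAS.
- Stoppers per arm: 0.15 × 85 = 12.75.
- Lost from the FAS with the first recording on Day 28: 12.75 × 27/84 = 4.10.
- Remaining: 12.75 − 4.10 = 8.65. FAS per arm: 85 − 4.10 = 80.90. Share: 8.65 / 80.90 = 10.7%.

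| First recording | ETD values per arm in FAS | Share of FAS |
|---|---|---|
| Day 25 | 9.11 | 11.2% |
| Day 28 | 8.65 | 10.7% |
| Day 31 | 8.20 | 10.2% |

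At 10% dropout the share is about 7%; at 5% it is about 3% to 4%.

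Some of these values are late enough to count as Week 12 under Table 2. Stops on Days 71 to 84 make up 12.75 × 14/84 = 2.1 per arm. That leaves about 8.65 − 2.13 = 6.5 per arm, or 6.5 / 80.90 = 8% of the FAS, whose values would move. The number is a little lower if some who stop just before Day 71 attend ETD on or after it.

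**4. Effect on an LCQ contrast (illustration).** Assume completers improve by 3.0 on serlopitant and 2.0 on placebo, and stoppers show no change at ETD.
- Equal 15% dropout: 3.0 × 0.893 − 2.0 × 0.893 = 0.89, against 1.0.
- 15% on serlopitant, 8% on placebo. Placebo stoppers: 0.08 × 85 = 6.80. Lost from the FAS: 6.80 × 27/84 = 2.19. Share: 4.61 / 82.81 = 5.6%. Contrast: 3.0 × 0.893 − 2.0 × 0.944 = 0.79.
- Counting only stops before Day 71, the serlopitant share is 8.1% and the placebo share is 6.80 × 43/84 / 82.81 = 4.2%. The contrasts are 0.92 with equal dropout and 3.0 × 0.919 − 2.0 × 0.958 = 0.84 with unequal dropout. Rounded, both readings give about 0.9 and 0.8.

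**The case against.** The SAP labels the visit openly as Day 85/ETD, and the LCQ, PGIC and CGIC endpoints name no week, unlike the cough and VAS endpoints. A summary at end of treatment that includes stoppers is a recognised choice. The completer difference used as the yardstick above itself conditions on stopping after randomization. Restricting CGIC to late values would remove most early stoppers and raise a selection problem of its own.

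Much of this stands for CGIC and, in part, for PGIC: a pooled table is defensible if the reader can see what is in it. It does not rescue LCQ. That endpoint enters a by-visit repeated-measures model patterned on Days 28, 56 and 84, and Protocol Table 4 lists LCQ and PGIC at Day 84, so the third visit is plainly meant as the 12-week one. The ± 3 days shown for this column in SAP Appendix C does not help. It is a study-visit window, it cannot fit an early ETD visit, and it excludes no data.

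Two stronger readings are tempting, and the documents support neither. A reader might infer that someone who stops after a few days, say on Day 10, supplies a Week 12 value. Such a subject normally has no on-treatment recording and is outside the FAS. A reader might also take the full 15%, about 26 of 170, as affected. That ignores the FAS rule, and subjects who withdraw consent or are lost to follow-up may never attend ETD.

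**Conclusion.** The point holds for subjects who stop between about Week 4 and Week 12. Under the assumptions of uniform stop days and full ETD attendance, about 8 to 9 per arm (10% to 11% of the FAS) have an ETD value pooled with Day 85 at 15% dropout. About 6 to 7 of them are too early for the SAP's own Week 12 range. The LCQ distortion, about 0.9 or 0.8 in place of 1.0, depends on assumed changes. Its direction in practice depends on who stops and when. With equal dropout the illustration shows dilution of the difference, not a false gain for serlopitant.

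It would be wrong to infer that a confirmatory result is at risk. All three endpoints are other secondary endpoints outside the hierarchy in SAP 8.7. The primary and key secondary cough endpoints have study-day windows, and the VAS endpoint has its own Day 84 assessment. The plan should be corrected, but its main conclusions do not turn on this.

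**What to change.** In SAP 7.3:

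- **LCQ and PGIC.** Assign values from the Day 85/ETD visit by study day, using the Table 2 ranges. Where a window already holds a scheduled value, keep that value.
- **Follow-up sentence.** State that the sentence below Table 2 classing every assessment after the last dose as follow-up does not apply to these endpoints. Day 85 comes after the last scheduled dose on Day 84, so without this exemption completers' Day 85 values would become follow-up and leave Week 12.
- **CGIC.** Keep the pooled table, and beside it report Day 85 and ETD values separately. Restricting CGIC to late values is a choice of estimand that this correction need not make.

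The cost is a few sentences, a little extra programming on a derivation already needed for cough data, and fewer subjects in the Week 12 LCQ and PGIC results. The Day 28 range (Days 2 to 42) is wide, so some mixing of durations can remain in the earlier columns. Keeping the scheduled value where one exists limits it.
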